FEDERAL UNIVERSITY OF BAHIA

[name]

NINTENDO WII AND EXERCISES AT REHABILITATION OF INDIVIDUALS WITH PARKINSON'S DISEASE

STUDY PROTOCOL AND STATISTICAL ANALYSIS PLAN

NCT03235284

Salvador 11/09/2019

Intervention

Interventions were conducted in all groups for 50 minutes a day, twice a week for 8 weeks, accounting for 16 total sessions. All activities were performed under the direct supervision of trained physiotherapists, and assessments and interventions always occurred 1 hour after Levodopa (on-period) administration.

Virtual rehabilitation with NW was performed in a room with an area of 20m2, equipped with the NW system (Nintendo Company, Minami-ku-based, Kyoto, Japan) and a multimedia device that projected the image on the wall at a height of one meter and twenty centimeters. In addition, the NW Wii Balance Board (WBB) platform(used for Wii Fit gaming) was used, in which it has four pressure sensors that detect the movements of the player standing on it in the orthostatic position, instantly demonstrating the position of the feet, the weight distribution and the displacement of the center of mass18.

GNW performed 40 minutes of training with NW, where patients played 4 games (Wii Sport and Wii Fit) standing up. In the first session, they played Boxing and Soccer Heading, and in the second session Golf and Running. Each game was held for 20 minutes with intervals of 1 minute rest every 5 minutes of activity. The games were chosen to facilitate lateralization, rotation and extension of the trunk, mobility of the upper limbs, transfer of weight, equilibrium reactions and stationary gait.

The ECs were performed through diagonal, active-assisted and resisted active movements, based on the proprioceptive neuromuscular facilitation (FNP) patterns in the upper limbs, scapula, pelvis and lower limbs. The protocol was also composed of gait training, in which the "gait cycle" was performed, where the physiotherapist offered a manual resistance to the hip during the step movement.

The GEC performed 40 minutes of exercises with objectives similar to the GNW group. During each session, 30 minutes of specific diagonals were performed, being upper limbs (flexion- abduction-external rotation / extension-adduction-internal rotation); scapula (elevation and posterior depression), pelvis (anterior elevation / posterior depression), lower limbs (flexion-abduction-external rotation / internal extension-adduction-rotation), 10 minutes of orthostasis gait training or trunk extension training in Ductus dorsal, always respecting the interval of 1 minute of rest every 5 minutes of activity. In the first weekly session the exercises were performed for scapula, upper limbs and trunk, while in the second session exercises for pelvis, lower limbs and gait.

In GNWEC, the combination of therapies was administered for 40 minutes, with 20 minutes of training with NW and 20 minutes of EC. Each intervention was applied in a similar way to the other groups, and the games or exercises were distributed according to the weekly session. In addition, all groups performed muscle stretching of the upper and lower limbs for 10 minutes

before initiating the interventions, and all patients were verbally oriented and stimulated by the therapist to perform the activities.

2.2. Primary outcome

The primary outcome was the functional balance, which was evaluated through the Berg Balance Scale (BBS). This ferment is composed of 14 items, graduated from 0 to 4 points that allow to measure the balance through progressively more challenging tasks. It presents a total score varying from 0 to 56 points, and a higher score reflects a better body balance.

2.3. Secondary Results

The gait was evaluated through the Dynamic Gait Index (DGI) scale, a tool composed of 8 tasks, a score ranging from 0 to 3 points, involving gait in different sensory contexts, reaching a maximum score of 24 points.

The Timed "Up & Go" test (TUG) was also used to assess functional mobility, in which this test measures in seconds the time it takes for an individual to lift a standard armchair, walk a distance of 3 meters, walk back and sit again. The longer the time to perform the activity, the greater the physical mobility deficit.

Quality of life was assessed using the Parkinson's Disease Questionnaire (PDQ-39), which consists of 39 items divided into 8 domains: mobility, daily living activities, emotional wellbeing, stigma, social support, cognition, communication and bodily discomfort. The total score varies from 0 to 100, in which a lower score denotes a better perception of the patient's quality of life.

2.4 Statistical analysis Plan

Data were analyzed using statistical software SPSS 21.0 27. A descriptive analysis (mean, standard deviation, median and interquartile range for quantitative variables, and absolute and relative frequency for qualitative variables) was performed to identify the characteristics of the study sample. To test the existence of pre and post intervention differences, as well as between each group, in balance, mobility and quality of life, a mixed ANOVA of repeated measures was used. In addition, distribution symmetry and the Shapiro-Wilk test were performed to identify the normality of the data. The level of significance adopted for this study was 5%.

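### The between-group test uses no baseline covariate: group x time is a valid change-score test, but ANCOVA on the same data is usually more precise if allocation was random

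*Combined protocol and SAP*

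**What the plan says.** The combined protocol and SAP describes three groups in its account of the interventions: Nintendo Wii ("GNW performed 40 minutes of training with NW"), exercises ("The GEC performed 40 minutes of exercises with objectives similar to the GNW group") and both ("In GNWEC, the combination of therapies was administered for 40 minutes"). The primary outcome is the Berg Balance Scale (BBS) total, which runs from 0 to 56 (section 2.2).

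Section 2.4 holds all the inferential text. It begins "To test the existence of pre and post intervention differences" and continues "as well as between each group, in balance, mobility and quality of life, a mixed ANOVA of repeated measures was used". It adds: "The level of significance adopted for this study was 5"%.

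Only a pre and a post measurement are mentioned. Section 2.4 names no covariate and does not say which term of the mixed ANOVA carries the between-group comparison. The supplied text gives no allocation method, sample size, SD, target effect or pre-post correlation. Section 2.4 is written in the past tense.

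**The concern.** A mixed ANOVA with one between-patient factor (group) and one within-patient factor (time) has three effects: group, time and group x time. The term that compares the groups on their response is group x time. With two time points it equals a comparison of mean change, so each patient's post score is adjusted by subtracting the whole baseline score. That is right only if the slope of post on pre is 1. When the slope is below 1, subtraction over-corrects and adds noise.

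Precision is at stake, not validity. In small arms a wider interval can hide a real difference in balance. There is also a conditional effect: in any one trial, a chance imbalance at baseline moves the change-score contrast in a predictable direction, and ANCOVA removes that movement.

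**Working it through.** **Inputs.** From the documents: three groups, two time points, alpha 5%, BBS 0 to 56. Assumed, because the documents give none: n per arm 8 to 20, pre-post correlation rho 0.5 to 0.95, SD ratio r = SDpost/SDpre of 0.8, 1 or 1.2, and random allocation. The plan has no figure of its own to reproduce.

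**Step 1: identity.** On one simulated data set (three arms of 15), the group x time F of the mixed ANOVA was 4.4122 and the one-way ANOVA F on change scores was 4.4122. They are the same test.

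**Step 2: variance per patient, in units of SDpre squared.**
- Change score: 1 + r² − 2·rho·r
- ANCOVA residual: r²(1 − rho²)
- Difference: (1 − rho·r)²

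The difference is never negative. Before the cost of estimating the slope, ANCOVA is at least as precise, and the two tie when rho·r = 1.

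**Step 3: cost of estimating the slope.** With three arms and N = 3n, the ANCOVA variance is multiplied by 1 + 1/(N − 5):
- 8 per arm: 1 + 1/19 = 1.053
- 10 per arm: 1 + 1/25 = 1.040
- 15 per arm: 1 + 1/40 = 1.025
- 20 per arm: 1 + 1/55 = 1.018

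This is the largest possible loss, about 2 to 5%. It occurs only if rho·r = 1.

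**Step 4: ANCOVA/change variance ratio, equal SDs.** The ratio is (1 + rho)/2 × [1 + 1/(N − 5)]. For example, at rho 0.5 and 15 per arm: 0.75 × 1.025 = 0.77.

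| n per arm | rho 0.5 | 0.7 | 0.8 | 0.9 | break-even rho |
|---|---|---|---|---|---|
| 8 | 0.79 | 0.89 | 0.95 | 1.00 | 0.90 |
| 15 | 0.77 | 0.87 | 0.92 | 0.97 | 0.95 |
| 20 | 0.76 | 0.87 | 0.92 | 0.97 | 0.96 |

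At 15 per arm, the square roots of these ratios make confidence intervals about 12%, 7%, 4% and 1% narrower.

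**Step 5: unequal SDs, 15 per arm.**
- r = 1.2: 0.89, 0.99, 1.02, 1.00 at rho 0.5, 0.7, 0.8, 0.9. At rho 0.8: 1.44 × 0.36 / (2.44 − 1.92) × 1.025 = 1.02.
- The r = 1.2 pattern is not monotone. At rho 0.95 and 8 per arm the ratio is 1.44 × 0.0975 / (2.44 − 2.28) × 1.053 = 0.92, so the gain returns once rho·r is clearly above 1.
- r = 0.8: 0.59, 0.64, 0.66, 0.62. A slope of 1 cannot be reached here, so 0.66 is about the worst case.

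**Step 6: level and power.** 5,000 simulations per case, 15 per arm, equal SDs, an assumed 0.8 SD effect in one arm.

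| rho | null rejection: group x time / ANCOVA | power: group x time / ANCOVA |
|---|---|---|
| 0.5 | 4.5% / 4.6% | 58% / 69% |
| 0.7 | 4.1% / 5.0% | 82% / 87% |
| 0.9 | 4.9% / 4.8% | 99.9% / 99.9% |

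**Step 7: shift from a chance baseline difference D.** The change-score contrast moves by (rho·r − 1)·D. For an arm 0.4 SD lower at baseline (D = −0.4):
- r = 1: +0.20, +0.12, +0.08, +0.04 SD at rho 0.5, 0.7, 0.8, 0.9.
- r = 1.2, rho = 0.9: (1.08 − 1) × (−0.4) = −0.03 SD. The sign reverses.

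The chance that a given pair of arms differs by more than 0.4 SD at baseline is 2[1 − Φ(0.4/√(2/n))]: 42%, 27% and 21% at 8, 15 and 20 per arm.

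**The case against.** The strongest reply is that nothing here is wrong with the test. Under random allocation group x time is unbiased and keeps its level, and it is the usual between-group term in a pre/post mixed ANOVA. Choosing ANCOVA is then an efficiency preference. It rests on an allocation method that the supplied text does not give and on assumed values of n, rho and SD ratio. The uncapped results above run from a clear gain (0.59) to a small loss (1.05). All of this stands, and it limits the point to precision.

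A reader might infer four stronger things that the documents do not support:
- *That the mixed ANOVA is invalid or biased.* The identity and the null simulations show otherwise.
- *That the group main effect will be read as the treatment comparison.* That term averages the pre-treatment score into the outcome and halves a true effect. Its simulated power in the cases of step 6 was only 22%, 20% and 19%. But section 2.4 does not say that it would be used; not naming the term is missing detail.
- *That the arm starting lower on BBS always looks better.* This holds only when rho × SDpost/SDpre is below 1.
- *That the trial was not randomised.* The supplied text is silent on allocation, and silence there is not evidence either way.

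**Conclusion.** The point holds as one of precision. The planned between-group analysis uses baseline only by subtraction, and ANCOVA would use the same pre scores better in most plausible settings. With equal SDs and an assumed 15 per arm, the variance falls by about 23%, 13%, 8% and 3% at rho 0.5, 0.7, 0.8 and 0.9. There is little or no gain when rho × SDpost/SDpre is near 1, and the loss there is at most 2 to 5% (20 down to 8 per arm).

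This rests on random allocation, a common linear slope and assumed inputs. The documents cannot show how much this trial would gain. If allocation was not random, change scores and ANCOVA can answer different questions, and the precision argument does not choose between them.

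**What to change.** Which change applies depends on two facts that the sponsor should state: how patients were allocated, and whether the data have been analysed.

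- **Random allocation, data not yet analysed.** Make ANCOVA the single between-group test and keep group x time of the mixed ANOVA as the supporting result. Suggested text for section 2.4:

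> Groups are compared on BBS by ANCOVA, with the post-intervention score as outcome, group as factor and the baseline score as covariate. Adjusted pairwise differences are reported with 95% confidence intervals. The group x time term of the mixed ANOVA is reported as a supporting result.

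  Do likewise for TUG, PDQ-39 and DGI where a baseline was recorded.

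- **Random allocation, data already analysed** (the past tense of section 2.4 suggests this). Reverse the order: keep group x time as the original analysis and report ANCOVA beside it, labelled as added later.
- **Allocation not random.** Keep group x time only.
- **In every case.** State that the group main effect is not the treatment comparison.

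The cost is a sentence or two per outcome and one residual degree of freedom, with no new data where a baseline exists. The main statistical price is an assumed common linear slope on a scale capped at 56, which should be acknowledged.

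### Does the analysis plan leave the Dynamic Gait Index without a between-group test?

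*Combined protocol and SAP*

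**What the plan says.** Section 2.2 makes functional balance, measured by the Berg Balance Scale (BBS), the primary outcome. Section 2.3 then lists three secondary outcomes in order:

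- gait: "The gait was evaluated through the Dynamic Gait Index (DGI) scale", with a maximum score of 24;
- the TUG, timed in seconds, which "was also used to assess functional mobility";
- quality of life: "Quality of life was assessed using the" PDQ-39, scored 0 to 100.

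Section 2.4 gives the purpose of the inferential analysis, "To test the existence of pre and post intervention differences, as well as between each group", and then its scope and method: "in balance, mobility and quality of life, a mixed ANOVA of repeated measures was used". The rest of that section covers the software, a descriptive analysis that "was performed to identify the characteristics of the study sample", a normality check and a 5% significance level. Neither gait nor the DGI is mentioned in section 2.4.

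**The concern.** Matched label by label, four outcomes are defined and three are tested. Section 2.3 ties functional mobility to the TUG and gait to the DGI, so *mobility* in section 2.4 looks like the TUG alone. The descriptive analysis concerns sample characteristics and does not fill the gap.

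If the DGI were really outside the plan, two things could follow. The trial might give no answer on gait, although the exercise programme contains gait training and the games were chosen partly to encourage stationary gait. Or a DGI comparison might be run, and reported or not, once the results were known. A SAP exists to prevent such selective reporting. The number of tests would also be uncertain.

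**Working it through.** The plan gives no figure to reproduce here. The check sets the outcome definitions beside the analysis sentence.

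| Outcome (2.2, 2.3) | Instrument | Matching word in 2.4, narrow reading | Matching word in 2.4, broad reading |
|---|---|---|---|
| Functional balance (primary) | BBS, 0 to 56 | balance | balance |
| Gait | DGI, maximum 24 | none | mobility |
| Functional mobility | TUG, seconds | mobility | mobility |
| Quality of life | PDQ-39, 0 to 100 | quality of life | quality of life |

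**Coverage.** Narrow reading: 4 − 3 = 1 outcome not named. Broad reading: 4 − 4 = 0.

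**Is *mobility* reserved for the TUG?** No. The Intervention section uses the word for the upper limbs. Section 2.3 uses it twice for the TUG, each time with a qualifier (functional, physical), and once more as the name of a PDQ-39 domain. Section 2.4 uses it bare. The document never says that mobility includes gait, and never says that it excludes it.

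**What kind of list is it?** Section 2.4 names none of the BBS, DGI, TUG or PDQ-39. It lists constructs in summary, so the absence of the letters DGI is no sign of exclusion. Nothing in the section says that only three outcomes are tested.

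**What would an analyst do?** The DGI is a listed secondary outcome and a numerical score in the same three groups (GNW, GEC, GNWEC). The purpose in section 2.4, before-and-after and between-group differences, fits it exactly as it fits the other scores. The normality check and the 5% level are stated for the data and the study as a whole. The plan offers no other inferential method, so the natural step is the same mixed ANOVA.

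**Does the number of tests matter?** Three groups give 3 × 2 / 2 = 3 pairwise comparisons per outcome: 3 × 3 = 9 for three outcomes and 4 × 3 = 12 for four. Section 2.4 specifies no pairwise procedure and no multiplicity rule, so neither total sets a threshold or alters a result.

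**The case for a change.** The best case for a change is that the narrow reading is the more literal one. Section 2.3 gives the two tests separate labels, and a SAP should use its own labels consistently. Even if *mobility* takes in both tests, one word then stands for two instruments on different scales, and the plan does not say that each is tested. Gait is a target of treatment, and naming four instruments would cost one line.

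Part of this stands. Section 2.4 does not state explicitly that the DGI is included, and naming the instruments would be clearer.

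The consequences claimed for it do not stand. The text describes interventions, assessments and analysis in the past tense, so rewording the sentence now could not restore pre-specification or remove a choice already made. The protection that exists is in section 2.3: because the DGI is listed there as a secondary outcome, a reader can see whether its result has been reported. The broad reading also has some support in the text, since the TUG is introduced, directly after the DGI, as a test that was also used.

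**Conclusion.** The concern does not call for a change. The wording is loose for one of three secondary outcomes (one of four overall), and only on the narrow reading of *mobility*. Analysts would fill the gap by applying the stated mixed ANOVA to the DGI. The primary BBS analysis is covered on any reading, and no number, rule or primary conclusion in the plan is wrong.

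This rests on two assumptions. The first is that the DGI was assessed before and after treatment like the other outcomes; the document gives no separate timing for any instrument. The second is that its listing in section 2.3 means it was to be analysed and reported. The document alone cannot show whether that was done.

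### The planned pre/post ANOVA uses only patients with both scores and compares unadjusted change, with no analysis set or sensitivity analysis, so selective loss that differs by arm can bias the group comparison

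*Combined protocol and SAP*

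**What the plan says.** Section 2.4 of the combined protocol and SAP contains the whole inferential plan. The aim is given as "To test the existence of pre and post intervention differences, as well as between each group, in balance, mobility and quality of life", and for this "a mixed ANOVA of repeated measures was used". On software it says only "Data were analyzed using statistical software SPSS 21.0", without naming a procedure. The other elements are descriptive statistics, a normality check and a 5% significance level.

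The Intervention section describes three arms (video games, manual exercises, or both), delivered "twice a week for 8 weeks, accounting for 16 total sessions". Section 2.2 makes the Berg Balance Scale (BBS, 0 to 56) the primary outcome.

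The available text does not state:
- which patients are analysed, or in which group;
- how a missing post score is handled;
- whether patients who stop attending are still assessed;
- how many patients were planned, lost or expected to be lost.

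**The concern.** A between-within ANOVA on one pre and one post score needs both values from each patient. A patient with a baseline only contributes nothing, and nothing in the plan counteracts that default.

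The patients who remain are compared on raw change. Change depends on baseline through regression to the mean, so losing patients by baseline balance from one arm alters that arm's mean change even when treatment has no effect. Losing patients because they are not improving alters it more directly.

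Loss before the final assessment is plausible over 16 supervised sessions. The arms differ in content, so reasons for leaving could differ too, and poor balance may itself make attendance harder. At stake is a spurious or hidden difference between arms on the BBS.

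**Working it through.** **The plan's own figures.** The only arithmetic in the text is 2 sessions × 8 weeks = 16 sessions, which is consistent. No sample size, power or dropout figure exists to reproduce, so the rest is illustration.

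**Step 1: what the method tests.** With two time points, the group-by-time F test equals a one-way ANOVA on change (post − pre) among patients with both scores.

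**Step 2: assumptions, none from the documents.** Pre and post scores are normal with SD 1 and correlation ρ = 0.5 to 0.8. There is no true group difference. A fraction d = 0.13 to 0.33 is lost from one arm and nobody from the others.

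**Step 3: bias in the change comparison.** Removing the lowest d of a standard normal variable moves the mean of the rest up by m = φ(z_d)/(1 − d), where φ is the standard normal density and z_d its d-quantile. This gives m = 0.243 at d = 0.13 and m = 0.541 at d = 0.33.

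- Loss of the lowest baselines: bias = −(1 − ρ)m. From 0.2 × 0.243 = 0.05 to 0.5 × 0.541 = 0.27 in size. The arm that loses patients looks worse.
- Loss of the smallest changes: bias = √(2(1 − ρ)) × m. From 0.632 × 0.243 = 0.15 to 1 × 0.541 = 0.54. The arm that loses patients looks better.
- Loss of the lowest post scores: bias = (1 − ρ)m, so 0.05 to 0.27. That arm again looks better.

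**Step 4: the same patients, post score adjusted for baseline (simulation).**

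| Loss in one arm depends on | Change comparison, absolute bias (SD) | Baseline-adjusted, absolute bias (SD) |
|---|---|---|
| Baseline | 0.05-0.27 | about 0 |
| Change | 0.15-0.54 | 0.14-0.43 |
| Post score | 0.05-0.27 | 0.10-0.43 |
| Nothing (random) | about 0 | about 0 |

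With the same selective loss in both compared arms, bias in their difference is about 0.

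**Step 5: softer selection.** Step 3 assumes that exactly the lowest patients leave. If loss is only partly driven by poor change (the standardised change plus an equal amount of noise), 20% lost from one arm gives a bias of 0.16 SD at ρ = 0.8 and 0.22 SD at ρ = 0.6.

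**Step 6: false-positive rate at a nominal 5%.**
- Softer selection on change, ρ = 0.7, 15 to 30 per arm: 7-8% at 10% loss, 9-13% at 20% and 11-22% at 30%.
- Exact selection on change, ρ = 0.5-0.8, 15 to 20 per arm, 13-33% lost: about 9-35%.
- Exact selection on baseline, same settings: about 5-12% for change and 4-5% with baseline adjustment.
- No loss or random loss: 4.8-5.7%, within simulation error of 5%.

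**Step 7: precision.** Change has variance 2(1 − ρ), and the baseline-adjusted residual has variance 1 − ρ². Their ratio is (1 + ρ)/2, which is 0.75 at ρ = 0.5 and 0.90 at ρ = 0.8. Adjustment therefore lowers residual variance by 25% to 10%, with or without missing data.

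**The case against.** A reader might infer that the trial's comparison is biased by dropout. The documents do not support that. They report no dropout and expect none, and bias needs loss that is both selective and different between arms. The arms share session length, frequency, supervision and stretching, which weakens the presumption that loss differs. This objection stands: the bias is a possibility of unknown size.

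A reader might also say that only completers of the 16 sessions are analysed. That is too strong. A patient who misses sessions but has a post score stays in the ANOVA. The correct description is patients with both scores. Even that is inferred from the method, because the SPSS procedure is not named.

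The most serious technical objection is that changing the model is not a general cure. When loss depends on the post score, the baseline-adjusted estimate has roughly 1.6 to 2 times the bias of the change comparison. This stands, and it is why a sensitivity analysis must accompany the new model. It does not rescue the ANOVA, which is biased under all three selective mechanisms and less precise when nothing is missing.

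Two further limits stand. The text refers only to pre and post intervention and names no fixed final visit, and it does not describe random allocation. It is also written in the past tense and dated 2019, so recalling patients may no longer be possible. Section numbering starts at 2.2, so earlier design text may exist that is not visible here. None of this supplies the analysis set or missing-data rule that section 2.4 lacks.

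**Conclusion.** The point holds as a gap with a conditional consequence. The named analysis uses only patients with both scores, compares unadjusted change, and has no analysis set or sensitivity analysis to guard it. Whether the result is biased depends on missing post scores that the documents do not report.

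Under the assumed one-arm loss of 13-33% and correlation of 0.5-0.8, the bias would be 0.05-0.27 SD for loss related to baseline or post score, and 0.15-0.54 SD for loss of poor responders. The upper ends need a third of one arm lost, none lost elsewhere, and exact selection. At 20% loss with softer selection on change, about 0.16-0.22 SD is more realistic. The direction cannot be predicted, since baseline-related and response-related loss push opposite ways.

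The figures also assume roughly normal scores, whereas the BBS is capped at 56. The case for baseline conditioning rests on two firmer results: it removes bias from baseline-related loss, and it cuts residual variance by 10-25% at the assumed correlations.

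**What to change.** 1. **Analysis set.** State that every patient is analysed in the allocated group, using all available post scores whatever the number of sessions attended. If follow-up is still open, obtain the post-intervention assessment from patients who stop early. This is the only step that addresses outcome-related loss at its source. If follow-up is closed, use the post scores already held.
2. **Model.** Replace the ANOVA by a baseline-conditioned analysis: post score adjusted for baseline or, if allocation was random, SPSS MIXED on pre and post with a common baseline mean and group-by-time terms, so that patients with a baseline only are kept.
3. **Reporting.** Give the number of missing post scores and the reasons, by arm.
4. **Sensitivity analysis.** Shift the missing post scores by a stated range of amounts, separately by arm, and show when the conclusion changes. This is needed because the new model does not remove bias from outcome-related loss and can enlarge it when loss depends on the post score. Keep the both-scores change comparison as supportive only.

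The cost is SAP wording, a different SPSS procedure and one extra analysis, plus contact with patients who stopped early if that is still possible. No patients are added. The estimate may be less favourable if those who left did worse.

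### Does running Shapiro-Wilk without a stated consequence, and analysing TUG and BBS untransformed, undermine the planned mixed ANOVA?

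*Combined protocol and SAP*

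**What the plan says.** Section 2.4 (Statistical analysis Plan) sets out the inference in one sentence: for pre-post and between-group differences "in balance, mobility and quality of life, a mixed ANOVA of repeated measures was used". The significance level is 5%. The next sentence but one adds that "distribution symmetry and the Shapiro-Wilk test were performed to identify the normality of the data". No rule links that check to a choice of method, and no transformation or rank-based alternative is named. Medians and interquartile ranges appear only among the descriptive statistics.

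On the scales themselves, section 2.2 says of the primary outcome, the BBS: "It presents a total score varying from 0 to 56 points". Section 2.3 says of the TUG, a secondary outcome, that "this test measures in seconds the time it takes for an individual". Neither section gives a mean, an SD, a distributional shape or a share of patients at the ceiling. The documents state no sample size. The Intervention section describes three arms: Wii training (GNW), conventional exercises (GEC) and the two combined (GNWEC).

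**The concern.** A statistician reading section 2.4 has three reasons to stop.

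- With two time points, the group-by-time test of a mixed ANOVA depends on within-group changes. Normality of raw scores is a different question. Scores can fail Shapiro-Wilk when the changes behave well, and the reverse.
- A normality test with no stated consequence either does nothing or tempts someone to switch method once the result is known.
- Completion times are often right-skewed and a score capped at 56 can pile up at the top. A few slow patients could then dominate the error variance of TUG in seconds.

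If all this applied, TUG would lose power and the analysis of the primary outcome could be changed after the fact.

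**Working it through.** **Inputs.** From the documents: three arms, pre and post measurements, a mixed ANOVA, the 5% level, TUG in seconds, BBS from 0 to 56. Everything else below (arm size, median, spread, correlation, effect) is assumed. The plan has no figure of its own to reproduce.

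**Test.** With two time points and n patients per arm, the group-by-time F-test is a one-way ANOVA on the changes d:

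F = [n Σ(d̄_g − d̄)² / 2] / [ΣΣ(d_gi − d̄_g)² / (3(n − 1))], on 2 and 3(n − 1) degrees of freedom (2 and 42 at n = 15).

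**Step 1: is the planned test valid?** Simulations used 6,000 runs per setting and 10, 15 or 20 per arm, with all arms sharing one distribution under the null. The Monte Carlo standard error is √(0.05 × 0.95 / 6000) = 0.28 points.

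- Lognormal TUG, median 12 s, log-SD 0.2 to 0.7, correlation 0.7 or 0.85: type I error 4.1-5.3%. The values below 4.4% all occur at log-SD 0.7 and are on the conservative side.
- BBS capped at 56, latent mean 46 to 53, SD 6, correlation 0.8, with 6% to 34% at the ceiling: 4.4-5.2%.

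One reason is that differencing removes most of the skewness. At log-SD 0.35, raw TUG skewness of about 1.1 becomes about 0 in the changes.

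**Step 2: the claimed TUG power loss.** Assume lognormal TUG, log-correlation 0.8, 15 per arm, one arm faster by a ratio r. Then log-SD = √ln(1 + CV²), and the SD of log change is log-SD × √(2(1 − 0.8)). At CV 0.5 these are √ln 1.25 = 0.472 and 0.472 × 0.632 = 0.299. The standardised effect is δ = −ln r / 0.299, and the noncentrality is λ = 15 × (2/3) × δ².

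- r = 0.75: δ = 0.288 / 0.299 = 0.96, λ = 9.27, power on the log scale 75%.
- r = 0.90: δ = 0.105 / 0.299 = 0.35, λ = 1.24, power on the log scale 15%.

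Simulated power, with every input but r held fixed:

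| CV | 25% faster: raw / log | 10% faster: raw / log |
|---|---|---|
| 0.3 | 96% / 99% | 28% / 32% |
| 0.5 | 57% / 75% | 12% / 15% |
| 0.7 | 29% / 48% | 8% / 10% |

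At 25%, the gaps are 3, 18 and 19 points. At 10%, they are 4, 3 and 2.

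**Step 3: change the error scale.** Keep a skewed TUG baseline (median 12 s), but let changes have a constant SD of 2 s, with one arm improving by 2 s and post values floored at 2 s. On the raw scale λ = 15 × (2/3) × (2/2)² = 10, which gives 79%. Simulated at 15 per arm:

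| log-SD of baseline | raw | log |
|---|---|---|
| 0.2 | 79% | 76% |
| 0.35 | 79% | 71% |
| 0.5 | 79% | 66% |

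Logging now loses power, by about 2 to 12 points over 10 to 20 per arm.

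**Step 4: the BBS ceiling.** At 15 per arm with a 4-point effect, power falls from 83% to 77% with 6% at the ceiling, from 84% to 67% with 18%, and from 82% to 51% with 34%. This loss comes from truncated measurement. A reflected log gives 73%, 68% and 55%, a change of about −5 to +4 points. A permutation p-value would not recover that information either.

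**Step 5: does the check redirect anything?** With TUG log-SD 0.35, correlation 0.85 and 15 per arm, Shapiro-Wilk rejects the pooled raw baseline in 68% of trials and the change residuals in 23%. For BBS (latent mean 48, SD 7, 45 patients) the figures are 70% and 9%. So the two checks can disagree. Under section 2.4 as written, though, a rejection leads nowhere, because "a mixed ANOVA of repeated measures was used" whatever the check shows.

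**The case for a change.** The strongest reply does not rest on TUG power. A good plan says which quantity is checked and what follows. By the figures for Shapiro-Wilk above, a test on raw BBS could often reject while the model is adequate, and an unstated consequence leaves room for improvisation on the primary outcome. The direction of the TUG effect also depends on the scale on which changes are homogeneous, which argues for fixing that scale in advance.

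Part of this stands: the plan leaves the checked quantity and its consequence unstated. The step from there to a defect does not follow.

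- The plan names one method and no switch. A test that alters nothing cannot also be charged with altering the method. A parametric primary model not selected by a normality test is the very arrangement the concern recommends for BBS.
- The text refers to the data, which does not rule out residuals. Score-level checks are not irrelevant either. Section 2.4 also tests differences between groups, and that ANOVA term uses patient averages, whose shape follows the scores.
- Making log(TUG) compulsory is a trade-off. It gains power under one error structure and loses it under another, and the documents do not say which applies. Section 2.4 is in the past tense, so rescaling now could itself be a choice made after the data were seen.

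**Conclusion.** The concern does not hold. Followed as written, the plan gives group-by-time tests with type I error close to 5% under every skewed or capped setting tried, assuming equal arms of 10 to 20 and identical distributions under the null. That TUG is right-skewed and that BBS sits near its ceiling are assumptions from outside the documents. The TUG power loss affects a secondary outcome only. It ranges from large (18 points at CV 0.5 with a 25% effect), through small (2 to 4 points with a 10% effect), to reversed (2 to 12 points in favour of raw seconds when changes have constant spread). Any BBS power loss at the ceiling is a limit of the scale that a transformation hardly repairs. The silence on what is checked, and on what follows, is missing detail. Supplying it would leave the planned primary result as it is.
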